1. Protocol Title

Effect of GOCOVRI on Quantity and Quality of Gait in Parkinson's disease

2. Objectives

Aim I: Investigate the effect of GOCOVRI™ on activity levels in people with Parkinson's disease (PD) and Levodopa induced dyskinesia (LID)

Hypothesis I: We hypothesize that GOCOVRI™ will result in an increase of daily activity due to improvement in LID symptoms.

Primary outcome measures: Total number of steps and turns per day

Aim II: Investigate the effect of GOCOVRI™ on comprehensive measures of gait and balance quality in people with PD with LID

Hypothesis II: We hypothesize GOCOVRI™ may improve discrete characteristics of gait and balance that is evident even within the first hour of the day walking.

3. Background

Levodopa induced dyskinesia (LID) is a symptom of Parkinson's disease for which there are limited treatment options. LID leads to reduced quality of life, increased caregiver burden and an increased risk of falls (Rascol et al., 2015, Chapuis et al., 2005). GOCOVRI™ is an extended release capsule prescription medication shown to reduce LID in people with PD (Pahwa et al., 2017, Pahwa et al., 2018). However, a number of studies have identified an increase in falls in those on the active medication study arm but not the placebo arm (13% increase in active and 7% in placebo) (Pahwa et al., 2017). In order to understand this increase in falls, comprehensive measurements of quantity of activity (gait measured in the home environment) and quality of activity (comprehensive gait characteristics that may increase risk of falls) need to be assessed in participants taking GOCOVRI™. In addition, the evidence for the effect of GOCOVRI™ on gait and balance in PD is limited (Smulders et al., 2016).

4. Study Design

This is an open label study in which the participants with PD will know they are taking medication and the experimenters will know which study visits and 7 days of monitoring are baseline, prior to taking GOCOVRI, and which study visits and 7 days of monitoring are after taking maximum dose of GOCOVRI after 5 weeks. Subjects will be given Amantadine extended release for purposes of this study.

5. Study Population

a. Number of Subjects

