All paper and electronic data collection forms, videos from the balance sessions, and output of Mobility Lab system and Actiwatch will be coded and not use the subject's name or other PHI in the subject ID. All subject-identifying information will be uploaded immediately after test session (Mobility Lab system) or when returned after wearing sensors/Actiwatch at home, to be stored and managed securely on our laboratory database, located on an OHSU-approved secure server. Subject confidentiality will be maintained in accordance with HIPAA regulations. Only individuals who are specifically authorized to view PHI by the investigator will have access to information that could be used to identify the subjects. Data will be stored at minimum for five years after the final publication related this project, and at maximum, indefinitely, if subjects also sign our Balance Disorders Laboratory Data Repository consent form (eIRB# 7997).

b. Sharing of Results with Subjects

There is no plan to share results with the subjects, aside from availability of final published manuscripts.

c. Data and Specimen Banking

If subjects also sign our Balance Disorders Laboratory Data Repository consent form (eIRB# 7997), then their data will be stored indefinitely in the repository (located on secure OHSU server).

8. Data Analysis

Aim I: We will collect a number of metrics related to activity level (such as, percentage of the day spent active, number of steps per day/hour, number of turns per day/hour). In addition, we will collect metrics related to the quality of gait and balance (such as mean and variability of: stride length, percentage of time spent in double support, foot strike angle, turn angle, turn velocity). We will undertake analyses to determine which of our metrics are significantly different between Week 1 (before GOCOVRI) and Week 6 (after GOCOVRI) groups with paired t-tests (if data appear normally distributed) or nonparametric Wilcoxon signed-rank test (data not normally distributed). We expect to see the significant change in some of our metrics (e.g., number of turns per day, percentage of the day active, stride time variability) due to improvement in LID symptoms. This result would indicate that GOCOVRI helps increase the overall activity level in addition to improving LID symptoms.

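### Section 8 does not tie the Aim I activity conclusion to the two named primary outcomes: significant change in some metrics, a gait-quality metric among the examples, could support it with both primaries null

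*Combined protocol and SAP*

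**What the plan says.** Section 2 (Objectives) is specific about Aim I. It states "Primary outcome measures: Total number of steps and turns per day", and Hypothesis I is directional: the drug "will result in an increase of daily activity due to improvement in LID symptoms". Gait and balance quality belong to Aim II, which is to study the drug's effect "on comprehensive measures of gait and balance quality in people with PD with LID".

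Section 8 (Data Analysis), under Aim I, does not refer to primary outcomes. It gives an open list of activity metrics and continues: "In addition, we will collect metrics related to the quality of gait and balance", followed by an open list of those. All are then compared before and after treatment, by paired t-test or Wilcoxon signed-rank test, to "determine which of our metrics are significantly different between Week 1 (before GOCOVRI) and Week 6 (after GOCOVRI) groups". The anticipated finding is worded "We expect to see the significant change in some of our metrics", and the examples are "number of turns per day, percentage of the day active, stride time variability". The paragraph ends: "This result would indicate that GOCOVRI helps increase the overall activity level in addition to improving LID symptoms".

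No section ranks the metrics, states a significance level or sidedness, adjusts for multiple tests, says how many metrics must change, or requires a change in steps or turns per day.

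**The concern.** A reader who sees two primaries in Section 2 will assume that a statement that activity increased rests on them. Section 8 offers another route. The result that would indicate more activity is significant change in *some* of a pooled, open set of metrics.

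Of the three examples, one is a primary (turns per day), one is another activity measure (percentage of the day active), and one describes gait quality (stride time variability). Steps per day, the primary named before turns, is not among them. A change in stride time variability says how a person walks, not how much.

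The wording also asks only for change, so a significant decrease would meet it as readily as an increase. At stake is whether the study's main conclusion means what its objectives say, and how often it would be reached by chance.

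**Working it through.** **The passages side by side.**

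| Element | Section 2 | Section 8, Aim I |
|---|---|---|
| Outcomes behind the activity claim | Steps and turns per day | *Some* of all activity and gait-quality metrics |
| Direction | Increase | Change, direction not given |
| Number that must change | Not stated | Not stated |
| Place of gait quality | Aim II | Tested with the Aim I metrics; one is an example |

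The plan states no error rate, so there is no figure to reproduce. The following illustrates the size.

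**Inputs from the documents.** There are 12 participants, each compared with their own baseline (Sections 5a and 8). Section 8 lists 5 activity metrics: percentage of the day active, and steps and turns, each per day and per hour. It lists 10 quality metrics, the mean and variability of five measures. The total is 5 + 10 = 15. Stride time variability appears only among the examples and would make 16.

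**Assumptions.** Two-sided 0.05 per metric; paired t-tests; no true effect on any metric; one favourable tail of 2.5% per metric, although the documents give no favourable direction for some quality metrics; equal correlation between all metrics, from 0.9 to 0.

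**Closed form at zero correlation.** A primary is non-significant in either direction with probability 0.95.

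- At least one favourable of 15: 1 − 0.975^15 = 31.6%.
- Neither primary significant, at least one of the other 13 favourable: 0.95² × (1 − 0.975^13) = 25.3%.
- At least two favourable of 15: 1 − 0.975^15 − 15 × 0.025 × 0.975^14 = 5.3%.
- Neither primary significant, at least two of the other 13 favourable: 0.95² × (1 − 0.975^13 − 13 × 0.025 × 0.975^12) = 3.7%.
- At least one of the 5 activity metrics: 1 − 0.975^5 = 11.9%.
- At least two of the 5: 1 − 0.975^5 − 5 × 0.025 × 0.975^4 = 0.6%.

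**Simulation with correlation** (n = 12, 100,000 runs per column):

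| Reading of *some* | 0.9 | 0.7 | 0.5 | 0.3 | 0 |
|---|---|---|---|---|---|
| One or more of 15 | 7.8% | 13.8% | 19.1% | 24.3% | 31.5% |
| … with neither primary significant | 4.2% | 9.6% | 14.5% | 19.4% | 25.2% |
| Two or more of 15 | 5.4% | 7.3% | 8.2% | 7.9% | 5.3% |
| … with neither primary significant | 2.1% | 4.0% | 5.0% | 5.3% | 3.6% |
| One or more of the 5 activity metrics | 5.3% | 7.8% | 9.4% | 10.6% | 11.9% |
| Two or more of the 5 activity metrics | 3.1% | 2.8% | 2.2% | 1.5% | 0.5% |

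The benchmark is 2.5%, the chance that one directional test falsely shows an increase.

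**If the claim is tied to the two primaries.** With either sufficing under Holm, the rate at zero correlation is 1 − 0.9875² = 2.5%, falling to 1.9% at correlation 0.9. With both required, it is 0.025² = 0.1% at zero correlation and 1.4% at 0.9 if neither truly changes, and at most 2.5% if only one does.

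**Cost in sensitivity.** Let d be the mean paired change divided by the SD of the paired changes. Power is the probability that a noncentral t on 11 degrees of freedom, with noncentrality d × √12, exceeds the critical value. Setting it to 80% gives d = 0.89 at two-sided 0.05 and d = 1.01 at 0.025. Requiring both primaries with 80% joint power and equal effects needs d of about 0.95 (correlation 0.9) to 1.02 (independent).

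**The case against.** The strongest reply is that Section 8 states an expectation, not a decision rule, and that nothing in it withdraws the primaries or the predicted increase. Two of its three examples are activity measures, one of them a primary. That is fair. A reader might infer that the plan adopts a rule by which gait quality alone proves more activity. The documents do not say so, and it is the least natural reading. What stands is that no other sentence links results to conclusion, and this one bypasses the primaries.

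A second reply concerns size. *Some* is plural, and steps per day and per hour are unlikely to be uncorrelated, so the 25% and 32% figures come from the least favourable combination. This also stands. With two or more metrics required, the rates are far lower, and on the activity-only reading they fall below 2.5% at correlations of 0.5 or less.

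Third, a reader might infer from Section 8's Aim II text that gait and balance are left out of the first-hour analysis. They are not: that analysis covers activity and gait and balance alike. The mismatch with Hypothesis II lies mainly in the sentence on what is expected, which speaks of activity.

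Finally, in a 12-person, open-label, before-and-after study, multiplicity control cannot make a change attributable to the drug. True, but the plan intends significance tests and a conclusion from them, so the basis of that conclusion should still be fixed.

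**Conclusion.** The point holds and should be fixed before the data are analysed. Section 8 allows the Aim I activity conclusion with both primaries null, or partly on metrics that do not measure amount of activity, and without a stated direction. This rests on the text alone and on none of the calculations.

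The size is illustrative and depends on an assumed significance level, correlation, count of metrics and favourable tails. The false-claim rate exceeds 2.5% on most readings of *some*, but not on all. It would be wrong to say that the plan necessarily inflates the error; the supported statement is that the plan leaves the rate unfixed, anywhere from about 0.5% to 32% across the readings examined.

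**What to change.** In Section 8, Aim I:

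- Base the activity conclusion on an increase in total daily steps and total daily turns, Week 1 versus Week 6.
- State in advance whether either suffices (Holm, overall two-sided 0.05) or both are required (each at two-sided 0.05).
- Delete the inference from *some* metrics to overall activity.
- Report percentage of the day active and the per-hour counts as supportive estimates with 95% confidence intervals.
- Move the gait-quality metrics to Aim II. Report them and the first-hour results as exploratory estimates with 95% confidence intervals, and align the Aim II expectation sentence with Hypothesis II.

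This needs no new data or visits, but it has two costs. Detectable d at 80% power rises from 0.89 for a single test to about 1.01 at Holm's stricter step, or to 0.95 to 1.02 if both primaries are required. Daily totals also depend on hours worn, which the documents do not fix: Section 5d gives a ceiling of 10 hours, while Section 6 asks for a minimum of 8 and uses 5 hours a day in its threshold for repeating the week. The per-hour counts should therefore be shown beside the primaries.

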A total of 12 people with PD and LID will be recruited to the study. Primarily, participants are to be recruited from the OHSU Movement Disorders Clinic by [name]. In addition to this, we have a laboratory database of PD volunteers for which we have information on LID from previous studies and for which [name] will assist in reviewing. Finally, neurologists in the OHSU Movement Disorders Clinics will be alerted to the study by [name] so they can refer suitable participants.

b. Inclusion and Exclusion Criteria

Subjects will be included in the study if they have:

- 1) a confirmed diagnosis of idiopathic Parkinson's disease by a movement disorders specialist and in accordance with the UK Brain Bank Criteria, 2) Hoehn & Yahr scores of II-IV, 3) aged between 50-85 years

old, 4) subjective report of experiencing at least 1h/day (two, half-hour periods) of ON time with troublesome LID, 5) ambulation with or without aids (e.g., walker or cane), 6) ≥ 30 days of a stable regimen of anti-Parkinson medications that includes a levodopa dose administered ≥ 3 times daily 7) a stable dose of levodopa throughout the study and 8) no amantadine for a minimum of 30 days prior to enrollment in to the study.

Subjects will be excluded from the study if they have: 1) other medical conditions which significantly affect mobility e.g., neurological/musculoskeletal disorders, 2) orthostatic hypotension at screening (defined as a drop of ≥ 20 mm HG systolic and ≥ 10 mm HG diastolic at 2 or 5 minutes of quiet standing after 5 minutes of supine rest), 3) a major psychotic disorder, 4) contraindication to GOCOVRI™ at time of screening, especially renal impairment estimated by glomerular filtration rate (eGFR) < 50 ml/min/1.73 m²) as impaired renal function can increase the chances of adverse reactions to the study drug, 5) mild to severe cognitive impairment as measured by Montreal Cognitive Assessment (MoCA) score ≤ 23 , 6) concurrent use of immediate release amantadine, and 7) are pregnant or plan to become pregnant.

c. Vulnerable Populations

None. Gender, ethnic origin, and minority status are neither inclusion nor exclusion criteria. Women and minorities will be included in this study. Children under the age of 18 will be excluded from this study. Subjects will not have mild to severe cognitive impairment.

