We will use an open-label trial design in which 12 participants will be given GOCOVRI™ provided by Adamas Pharmaceuticals, Inc. [name] (PI) will sign the medication order and prescribe the doses and the medication will be administered by the OHSU research pharmacy. A research coordinator will pick up the medication from the pharmacy prior to the baseline study visit to give to the subject with instructions about when to start taking the medication and how to increase dose over time. The drug will be administered orally once daily before bedtime. A forced four-week titration will be prescribed with the active treatment arm receiving 137mg/day (2 pills) during weeks 2 and 3 which will be increased to 274mg/day (4 pills; unless dyskinesia is relieved by the lower dose; then will stay at initial dose – increase will be based on clinical response to the lower dose) for weeks 4, 5 and 6 (see Figure 1). Participants will be contacted by a research assistant after the dosage is increased to ensure there are no issues, which if reported will be followed up by [name]. In addition, participants will be encouraged to call a study team member if they are having difficulty tolerating the medication at any point during the study. If the subjects experience side-effects at higher dose, then they will be asked to continue at the 137mg/day until after the second assessment, then tapered off in a single week. If patients wished to continue on GOCOVRI we will reach out to their provider and share their interest in wanting to remain on the medication. It will be explained to patients that they will only be guaranteed to receive GOCOVRI during the course of the study and future use will be at their and their provider's discretion with cost as determined by their individual insurance and pharmacy providers.

Data collection

Prior to the first study visit, participants will go to the OHSU outpatient Laboratory or a local laboratory who will assess renal function (unless this test has previously been completed with in the 30 days prior

to the first study visit). If renal impairment (estimated glomerular filtration rate (eGFR) < 50 ml/min/1.73 m²) is found, subjects will be excluded from the study, and the subjects will be informed of the results and the results will be sent to their primary care physician. Subjects will complete a blood pressure test for orthostatic hypotension (OH). If OH is found, the person will be excluded from the study.

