Aim II: We will also separately examine the first hour of sensor data recording each day to see the overnight effect of GOCOVRI™ on activity and balance/gait. We will undertake analyses to determine which of our metrics are significantly different during the first hour of the day between Week 1 (before GOCOVRI) and Week 6 (after GOCOVRI) groups with paired t-tests (if data appear normally distributed) or nonparametric Wilcoxon signed-rank (data not normally distributed). We expect to see a significant change in metrics related to activity level especially during the first hour of the day before the levodopa intake as some subject with PD may have difficulty in initiating walking during the first hour of the day. This result would indicate that GOCOVRI is also helping patients to overcome the difficulty in initially walking during the first hour of the day before the levodopa intake.

Finally, we will explore the opportunity to identify which metrics of gait and balance best relate to LID and the medication fluctuations throughout the day to further understand how LID affects mobility.

9. Privacy, Confidentiality, and Data Security

Subject privacy. Recruitment will take place over the telephone with the researcher in a private office. Consenting will occur during a remote meeting prior to the first study visit with only study team member(s) present. Likewise, during the remote visits only study team members will be present.

Data privacy. Upon consent, a subject ID# will be assigned for a subject and all data files will only have this number on it – the ID number will not contain any of the 18 HIPAA identifiers. The file containing the link between subject name and ID# will be maintained on an encrypted lab computer, in an electronic-access office, and file will only be accessible by study team members who need it. After test session, electronic data will be uploaded to our laboratory database and in a web-accessible REDCap database that is located on a secure OHSU server. Any paper files will be kept in electronic-access only lab offices.

10. Provisions to Monitor the Data to Ensure the Safety of Subjects

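### Section 8 reads a significant before/after change in a single-arm, open-label study as evidence that GOCOVRI caused it, which the design cannot show

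*Combined protocol and SAP*

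**What the plan says.** Section 4 declares the design: "This is an open label study in which the participants with PD will know they are taking medication". It adds that the experimenters also know which monitoring week is which. Section 6 (Drug dosage) describes an "open-label trial design in which 12 participants will be given GOCOVRI", so there is one arm and everyone is treated. Section 5b enrols on a "subjective report of experiencing at least 1h/day (two, half-hour periods) of ON time with troublesome LID".

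The Aim I analysis in Section 8 asks which metrics are "significantly different between Week 1 (before GOCOVRI) and Week 6 (after GOCOVRI) groups with paired t-tests", with the Wilcoxon signed-rank test as the alternative for non-normal data. It expects some metrics to change, credits that change to better LID, and concludes: "This result would indicate that GOCOVRI helps increase the overall activity level".

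Aim II applies the same tests to the first hour of each day's recording, which it describes as a look at the drug's overnight effect. It concludes: "This result would indicate that GOCOVRI is also helping patients to overcome the difficulty in initially walking during the first hour of the day".

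No section names the missing control as a limit on these conclusions, and none calls them exploratory. The plan uses the language of exploration only for measuring dyskinesia with sensors (Section 6) and for relating gait metrics to LID and medication fluctuations (end of Section 8).

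**The concern.** The two concluding sentences in Section 8 are the only guidance the plan gives on interpreting the Aim I and Aim II tests. Both name the drug as the cause, without qualification. The quantity tested is the mean Week 6 minus Week 1 change, which is the drug effect plus everything else that changed over those weeks.

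The documents themselves supply several non-drug routes:

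- **Expectation.** Participants know they are treated, and they decide how much they walk.
- **Repeat sensor wear.** The first sensor week is when participants are learning the system, and it is always the untreated week.
- **Time.** The two weeks always fall in the same order, about five weeks apart.
- **Regression to the mean in LID.** Entry requires self-reported troublesome LID, and the plan treats LID as the driver of activity.

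If the plan is followed as written, a significant change will be written up as a drug benefit. Section 3 motivates the study by an increase in falls on active drug, and the timeline in Section 6 ends in a manuscript, so the wording of the conclusion matters.

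**Working it through.** **The plan's own figures.** There is nothing to reproduce. The plan gives 12 participants but no power, effect size, SD, alpha or success criterion.

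**What the design provides**

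| Feature that could separate drug from non-drug change | In the documents |
|---|---|
| Concurrent control or randomisation | None; all 12 receive drug (Section 6) |
| Masking of participants or experimenters | None (Section 4) |
| Repeated baseline | None; one baseline week |
| Off-drug sensor week after treatment | None; the drug is tapered to week 8 (Figure 1 caption), but no sensor week is scheduled then |

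**What the test tests.** For person i, D_i = (drug effect)_i + (non-drug change)_i. The paired t-test has the null hypothesis mean(D) = 0. Rejecting it says the sum is not zero and does not say which term is responsible. The Wilcoxon signed-rank test works on the same differences and has the same limit.

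**Illustration.** Inputs: n = 12 (Section 5a); two-sided alpha 0.05 (assumed); drug effect zero (assumed); non-drug drift d in SDs of the paired difference (assumed range).

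- Critical value: t(0.975, 11 df) = 2.201.
- Noncentrality: d × √12 = 3.464 d.
- P(significant) = P(|T| > 2.201), with T noncentral t on 11 df.

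| Assumed drift d | Noncentrality | P(significant), per metric |
|---|---|---|
| 0 | 0 | 5.0% |
| 0.1 | 0.346 | 6.2% |
| 0.2 | 0.693 | 9.7% |
| 0.3 | 1.039 | 15.8% |
| 0.4 | 1.386 | 24.5% |

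A drift of the same size against the drug gives the same percentages, but the significant results would then mostly point to worsening.

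**Would a control within 12 solve it?** Split 6 versus 6, using the normal approximation on change scores: power ≈ Φ(d√(6/2) − 1.96). At d = 1.0 this is Φ(1.732 − 1.960) = Φ(−0.228) = 41%. At d = 0.5 it is Φ(0.866 − 1.960) = Φ(−1.094) = 14%. A control arm inside the planned sample is not a workable remedy, which leaves the stated conclusion as the thing to change.

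**The case against.** The strongest reply is that the design is openly declared and that this is the ordinary limitation of any before/after study. An uncontrolled 12-person study is acceptable as a pilot. The plan also has real safeguards: levodopa is to be held stable, activity is measured by device, medication diaries are kept, and each person is their own control. These limit co-intervention, rater bias and stable between-person differences. None of them separates drug from time or expectation, so the point about attribution stands. Running the study is not in question.

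Three stronger readings are tempting, and the documents do not support them.

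- **A formal decision rule with an inflated error rate.** A reader might infer this from the two concluding sentences. They are the investigators' interpretation of a result they say they expect. Section 8 sets no alpha, primary test or success criterion, so there is no rule whose error rate can be computed. The paired t-test, under its usual assumptions, keeps its level for its own null of no mean change.
- **A false-positive rate shown to be well above nominal.** The percentages depend wholly on the drift assumed. At 0.1 SD the figure is about 6%, and at zero it is 5%. The documents give no drift, so the figures illustrate the problem and do not measure it.
- **All non-drug influences favour the drug.** Expectation has the clearest favourable direction. Novelty of the sensors could raise activity in the first week and so work against the drug. Enrolment is spread over months 2 to 6 in Table 1, so seasonal shifts need not be common to all participants. Selection is on LID, not on low step counts, so regression to the mean reaches steps and turns only indirectly, through a link the documents do not quantify.

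**Conclusion.** The interpretation in Section 8 is wrong as written. A significant Week 1 to Week 6 change would establish that the mean change is not zero. It would not establish that GOCOVRI caused the change, nor that improved LID was the mechanism, since no analysis of that link is attached to the Aim I claim. This conclusion rests on the design alone and needs no assumed number.

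How far a non-drug shift could mislead is unknown. Over assumed drifts of 0.1 to 0.4 SD, with an assumed two-sided 5% test and no drug effect, the chance of a significant result runs from about 6% to about 24% per metric. The net direction of the non-drug influences is also unknown. The fault is confined to the stated inference. The choice of paired test and the decision to run a small open-label study are not at fault on this point.

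**What to change.** In Section 8:

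1. Replace both concluding sentences ("This result would indicate that GOCOVRI helps increase the overall activity level" and "This result would indicate that GOCOVRI is also helping patients to overcome the difficulty in initially walking during the first hour of the day") with a statement that the result is the change from baseline during open-label GOCOVRI, reported as a paired mean change with a 95% CI.
2. In Aim I, drop or qualify the clause crediting the change to better LID. In Aim II, do the same for the phrase presenting the first-hour analysis as showing the drug's overnight effect. Changing only the two concluding sentences would leave these causal claims in place.
3. Add one sentence saying that, without a control, the change cannot be attributed to the drug as distinct from expectation, repeat sensor wear, time effects or regression to the mean in LID.

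Do not add a statement that the results serve to plan a controlled study, because the documents give the study no such purpose.

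The cost is a few sentences and a weaker stated conclusion. Conduct and sample size do not change.

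### Gait-quality and first-hour metrics are screened for significance from an open-ended list with no error-rate control; about 25 named tests give about 1.25 chance findings if nothing truly changes

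*Combined protocol and SAP*

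**What the plan says.** Section 2 (Objectives) names primary outcomes under Aim I only: "Primary outcome measures: Total number of steps and turns per day". Aim II has no lead outcome.

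Section 8 (Data Analysis), Aim I, describes the activity metrics by example: "such as, percentage of the day spent active, number of steps per day/hour, number of turns per day/hour". Gait and balance quality is treated the same way: "such as mean and variability of: stride length, percentage of time spent in double support, foot strike angle, turn angle, turn velocity". The analysis is meant to "determine which of our metrics are significantly different" between Week 1 and Week 6, "with paired t-tests (if data appear normally distributed) or nonparametric Wilcoxon signed-rank test (data not normally distributed". Among the changes it expects, the plan lists "number of turns per day, percentage of the day active, stride time variability". The last of these does not appear among the example metrics.

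Section 8, Aim II, repeats the rule for the first hour of recording: "We will undertake analyses to determine which of our metrics are significantly different during the first hour of the day". It then predicts a significant change in activity-level metrics in that hour, and says such a result would show the drug helping patients with early walking before levodopa.

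Section 8 gives no significance level, closed list of metrics, ranking of Aim II metrics or multiplicity adjustment. Only its closing search, for metrics that relate to dyskinesia and medication fluctuations, is described as exploring.

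**The concern.** The rule is to test each metric, see which ones pass, and then do the same in a second time window. The number of tests is not fixed, so the chance of a spurious finding is neither controlled nor known. Because the lists are illustrative, metrics can be added after data are seen, and stride time variability already enters outside the listed examples.

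What is at stake is the reading of Aim II. Section 3 (Background) motivates the study by an excess of falls on active drug, so a chance improvement in a gait metric would mislead on the question that prompted the work. The study has 12 participants, open-label treatment and no concurrent control that could expose a chance result.

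**Working it through.** **Inputs from the documents**
- Pairs: 12 (section 5a).
- Whole-day gait quality (section 8, Aim I): 5 features, each as mean and variability, give 10. Adding stride time variability gives 11.
- First hour (section 8, Aim II): the same 11 plus 3 activity metrics (time active, steps, turns) give 14. Within a single hour the per-day and per-hour counts merge.
- In scope: 11 + 14 = 25. Whole-day activity metrics, which include the two primary outcomes, are left out.

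**Assumptions, not in the documents**
- Two-sided 5% per test.
- No true effect on any metric.
- A common pairwise correlation between metrics, from 0 to 0.7.
- Paired t-tests throughout. The data-dependent switch to Wilcoxon is not modelled.

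The plan gives no error rate or test count, so there is no figure of its own to reproduce.

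**Expected false positives**, at any correlation: 25 × 0.05 = 1.25. For the first hour alone: 14 × 0.05 = 0.70.

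**At least one false positive, independent tests**, 1 − 0.95^m:
- m = 25: 1 − 0.95^25 = 0.723
- m = 14: 1 − 0.95^14 = 0.512
- m = 3: 1 − 0.95^3 = 0.143. Counting only favourable changes: 1 − 0.975^3 = 0.073

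**With correlation** (simulated paired t-tests, n = 12, no true effect; the zero-correlation row is from the formula):

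| Correlation | All 25 | First hour, 14 |
|---|---|---|
| 0 | 72% | 51% |
| 0.3 | 62% | 45% |
| 0.5 | 50% | 37% |
| 0.7 | about 35% | 27% |

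**Sensitivity to the level.** At 1% per test, 25 independent tests give 1 − 0.99^25 = 0.222, with 25 × 0.01 = 0.25 expected.

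**Effect of adjustment.** With Benjamini-Hochberg at 5% in each family (11 and 14 tests), the simulated chance of any false claim when nothing changes is about 10%, 9%, 8% and 5 to 6% at correlation 0, 0.3, 0.5 and 0.7.

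**Cost of adjustment.** Unadjusted, the observed change must reach 2.201/√12 = 0.64 SD of the paired differences. If only one of the 14 first-hour metrics truly changes, Benjamini-Hochberg requires roughly p ≤ 0.05/14 = 0.0036. That corresponds to t = 3.69 and 3.69/√12 = 1.06 SD. Power at a true change of 0.8 SD falls from 71% to about 26%.

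**The case against.** The strongest reply is that this is a 12-person open-label study whose primary outcomes sit under Aim I and whose second hypothesis is worded tentatively. Formal error control may be out of proportion, and an exploratory label with full reporting would do. That argument stands as a remedy, and the fix offers it. It does not describe the current plan, which reserves the language of exploration for its last analysis and attaches a drug-effect conclusion to first-hour significance.

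Correlation is the second reply, and it also has force. Means and variabilities come from the same sensors, and the first hour is part of the whole day. The 72% is therefore an upper-end figure for the named tests. At a correlation of 0.5 the chance is about even, and at 0.7 about 35%.

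Three stronger readings are tempting, and the documents do not support them:
- A reader might count 30 tests and quote 1 − 0.95^30 = 79%. That adds five whole-day activity metrics, including both primary outcomes, which belong to Aim I and not to this point.
- A reader might infer that any of the 14 first-hour hits would be taken as benefit. The conclusion in section 8, Aim II, follows from the predicted change in activity metrics. There the chance is about 14%, and a worsening could not support it.
- A reader might infer that only significant metrics will be reported. No section says so. The plan simply does not commit to reporting all of them.

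**Conclusion.** The concern holds in this form. Section 8 sets up an unadjusted screen of open-ended lists in two time windows. For the 25 named gait-quality and first-hour tests, about 1.25 false positives are expected. The chance of at least one runs from 72% down to about 35% as the correlation rises from 0 to 0.7. All of this assumes a two-sided 5% level and no true effect on any metric. A chance finding is not shown to be more likely than not at every plausible correlation, but throughout this range the risk is at least about seven times the nominal 5%.

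For the specific claim of early-morning benefit, the inflation is modest: about 14%, or 7% in the favourable direction. The true number of tests may be larger than 25, because the lists are open and the stance-balance measures in section 6 are not counted.

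**What to change.** Before any Week 6 file is processed, freeze the list of metrics and the algorithm settings and state the significance level. Report every metric tested, with its mean paired difference and 95% interval, whether or not it is significant. Then choose one of two rules:

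1. Call a metric changed only if it survives Benjamini-Hochberg at 5% within its family, the families being whole-day gait quality and first hour.
2. Label both screens exploratory, and remove from section 8, Aim II, the conclusion that the drug is helping patients whenever it would rest on an unadjusted result.

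Either choice needs only a change of analysis wording and trivial computation, with no added participants or data. The first has a real cost in power, shown above: from 71% to about 26% for a lone first-hour change of 0.8 SD. The second avoids that cost but gives up the claim. Neither addresses the uncontrolled before-after design, so a metric that survives adjustment would still not by itself establish a drug effect.
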